- Any uncontrolled medical condition expected to limit life expectancy or interfere with participation in the trial (i.e. unstable cancer, severe depression or anxiety by DSM-IV criteria)
- Abnormal stress test, as determined by the treating physician (unless cardiology clearance provided)
- Active substance abuse or alcohol dependence
- Uncorrected vision or hearing deficits that would preclude administration of the cognitive measures
- Unwilling or unable to provide written informed consent and do not have an appropriate proxy who is able to provide consent on their behalf
- History of fainting spells of unknown or undetermined etiology that might constitute seizures
- History of seizures, diagnosis of epilepsy, history of abnormal (epileptiform) EEG or family history of treatment resistant epilepsy
- No medication is an absolute exclusion from TMS. Medications will be reviewed by the responsible MD and a decision about inclusion will be made based on the following:

- The subject's past medical history, drug dose, history of recent medication changes or duration of treatment, and combination with other CNS active drugs.
- The published TMS guidelines review medications to be considered with TMS
- Any metal in the brain, skull or elsewhere unless approved by the responsible MD
- Any medical devices (i.e. Cardiac pacemaker, deep brain stimulator, medication infusion pump, cochlear implant, vagal nerve stimulator) unless otherwise approved by the responsible MD
- Substance abuse or dependence within the past six months
- Absence of corticospinal functional integrity
- Inability to provide informed consent or have an appropriate proxy provide consent on their behalf
- Age younger than 18 years
- Pregnancy
- Prisoners

6) Number of Subjects*

This is a single center study with 10 planned subjects.

7) Study Timelines*

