After having a potential research participant has been identified, we will call him/her to discuss the study and determine both eligibility and interest in participating in the study. Participants will undergo TMS safety screening to ensure that they are eligible to participate, following the TMS Safety Guidelines (Rossi et al. 2009). Participation will involve a pre-study fMRI scan to identify a target for TMS application, and pre-study neuropsychological testing. The proposed timeline of TMS will be 10 sessions over a 2-week period, followed by a second, post-TMS neuropsychological testing session to assess for improvement. Patients who do not have significant benefit or change in symptoms after the first 10 sessions of rTMS may be offered an additional 10 sessions where the brain region being targeted will be changed based on fMRI data and the investigators' clinical impression. We will then plan to follow up with patients at 1 month to assess duration of effects of the treatment. The patients will be re-scored using the Apraxia of Speech Rating Scale and will undergo a second neuropsychological testing battery. We will also identify any post-treatment adverse effects during this visit.

8) Study Endpoints*

The primary study endpoint will be improvement on the language performance measured by neuropsychological testing and the Apraxia of Speech Rating Scale (a tool designed to measure the presence and severity of apraxia of speech that uses a 5-point rating scale to assess 16 items (see attached material, [Strand et al.

2014]). We will also look at global activity levels of the brain utilizing single-pulses pre- and post- TMS.

9) Procedures Involved*

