Participants will undergo a pre-test assessment (consisting of neuropsychological performance and will be scored using the Apraxia of Speech Rating Scale). Following this visit, participants will receive 10 sessions of repetitive TMS in a 4 week period. After that, participants will undergo a post-test assessment in which they will be rescored using the Apraxia of Speech Rating scale and reassessed on neuropsychological testing. We will collect this information, along with demographic and basic medical information (age, gender, race, handedness, education level, and medical comorbidities) from the participants' medical records. This information will be important for reporting results (demographic information), scoring the neuropsychological testing (education level), and in determining eligibility to undergo TMS (medical comorbidities).

Single Pulse TMS

Prior to and following each TMS visit, a pre TMS side effects questionnaire will be performed..

We will use the TMS machine to assess the global activity levels of the brain utilizing single-pulses and to set the parameters for the repetitive TMS. TMS will be delivered using a biphasic figure of eight coil. This stimulation phase will consist of 3 batches of 30 TMS pulses delivered every 5-7 seconds at 120% of resting motor threshold (RMT). This is the standard way of setting the parameters of the TMS. We define the RMT as the intensity at which 5 responses are obtained (about 50 μV) when we give 10 stimulation pulses.

Repetitive TMS

Repetitive TMS will be delivered at 90% of the resting motor threshold at 20 Hz (50 trains, 40 pulses with 28 second inter-train interval), which was based on parameters used in prior studies including one prior case report in which rTMS was previously used and reported to lead to improvements in speech in an individual with PPAOS (Spagnolo et al. 2013), and two studies in which rTMS was used in primary progressive aphasia, a similar condition in which the same target was stimulated (Cotelli et al. 2012, Antezak et al. 2018).

10) Data and Specimen Banking*

We will not plan to collect or bank any specimens with this study.

11) Data Management*

There is only one document that lists the individual's name and the subject number that will be assigned to him/her upon giving informed consent to participate in this

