study. This document will be kept at the Principal Investigator's Office at [name]. Data will be stored for a minimum of 3 years, and in accordance with University Policies thereafter. We would like to keep de-identified data, so that other studies may benefit from these after study completion. De-identified data will be stored at the Professional Arts Center ([name]) and Clinical Research Building ([name]). It will be kept in a locked cabinet, and the only people who will have access to this data are personnel approved by the IRB to work on this study.

12) Provisions to Monitor the Data to Ensure the Safety of Subjects*

Data monitoring

Only authorized personnel will have access to the data collected during the study. Participants' information will not be shared with any party without IRB-approval. Research data will not be released to the participants.

Data collection will be halted if the participant requests it. If this occurs, subject will be taken off the study and the reason of discontinuation will be documented. Data collected before will be kept by the investigator.

Monitoring the safety of participants with respect to TMS

TMS has been used in a growing number of laboratories worldwide since 1984. A series of adverse events have been identified since then, and have been thoroughly reviewed for the development of recommended safety guidelines and precautions for the use of TMS, first at a consensus conference at the NIH in June, 1996 and, more recently, in 2008 in Siena (Italy), in a meeting of an international panel of TMS experts (The Safety of TMS Consensus Group).

The principal investigator will ensure that these guidelines are well-known by all study investigators and will carefully follow these updated safety guidelines in the present study.

13) Withdrawal of Subjects*

As the greatest risk to subjects with TMS as documented in prior literature, is seizure, the development of a seizure during or immediately following TMS will be grounds for withdrawal from the study. Similarly, the development of a new risk factor for seizure during the study period will be grounds for withdrawal (including new stroke/structural brain lesion, central nervous system infection such as meningitis or encephalitis, or traumatic brain injury).

Page 7 of 16

14) Risks to Subjects*

Risks associated with TMS:

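### Section 13 does not separate ending TMS from leaving the study, so no post-test or 1-month adverse-effect visit is provided for patients withdrawn after a seizure or a new seizure risk factor

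*Protocol*

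**What the plan says.** Protocol Section 13 (Withdrawal of Subjects) calls seizure the greatest risk of TMS and states that "the development of a seizure during or immediately following TMS will be grounds for withdrawal from the study". The next sentence, opening with *Similarly*, adds that "the development of a new risk factor for seizure during the study period will be grounds for withdrawal". Its listed examples are new stroke or structural brain lesion, central nervous system infection and traumatic brain injury.

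The planned assessments after treatment are in Sections 7 and 9. After the sessions, "participants will undergo a post-test assessment in which they will be rescored using the Apraxia of Speech Rating scale", together with neuropsychological testing. Section 7 continues: "We will then plan to follow up with patients at 1 month to assess duration of effects of the treatment". It adds: "We will also identify any post-treatment adverse effects during this visit".

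On data after a subject leaves, Section 12 covers the participant's own request to stop. Collection halts, the subject comes off the study and the reason is recorded. "Data collected before will be kept by the investigator". Section 26 says much the same for revoked authorization. Neither addresses a withdrawal under Section 13.

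**The concern.** Stopping an intervention and leaving a study are different acts, and only the first is needed to end exposure. Section 13 names only the second. A patient withdrawn under it has no assessment assigned afterwards, because the post-test and the 1-month visit are described for patients who are still participating.

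Whether later data exist would then depend on whether a bad event occurred. What is chiefly at stake is safety information: how the patient recovered, whether delayed effects appeared, and where speech and cognition stood afterwards. In a study of 10 patients, one such history may be the most informative safety observation it yields.

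**Working it through.** **Text check.** The Protocol gives no figure on this point to reproduce, so the main check sets the sections side by side.

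1. *What does withdrawal apply to?* The seizure sentence in Section 13 refers to the study. The risk-factor sentence omits those words, but *Similarly* and the section title carry the same meaning. Elsewhere the Protocol uses narrower terms: under Section 14, TMS is stopped for impending syncope and the session is ended for dental pain. Those are session-level stops, but they show that wording about stimulation alone was available.
2. *Is follow-up after withdrawal provided for?* No section describes an early-termination visit, safety follow-up or outcome assessment after withdrawal. Section 14 specifies an auditory referral after hearing complaints. No comparable later assessment is specified after a seizure.
3. *What is still captured?* Section 14 has a neurologist present during TMS, and Section 9 states: "Prior to and following each TMS visit, a pre TMS side effects questionnaire will be performed". The seizure itself would therefore be recorded.
4. *What may be missed?* For an event during the first 10 sessions, both the post-test and the 1-month visit still lie ahead. For an event after the post-test, only the 1-month visit does.

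**Scale.** Inputs:
- n = 10 (Section 6: "This is a single center study with 10 planned subjects").
- Seizure risk p below 0.001 for repetitive TMS (Section 14, unit not stated).
- 10 sessions per patient, or 20 if the optional further course in Section 7 is given.

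Each withdrawn patient is 1/10 = 10% of the planned sample.

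The chance of at least one seizure is 1 − (1 − p)^m, at the upper bound p = 0.001:

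| Reading of the risk | m | Chance of at least one |
|---|---|---|
| Per patient | 10 | 1 − 0.999^10 = 1.0% |
| Per session (assumed), 10 each | 100 | 1 − 0.999^100 = 9.5% |
| Per session (assumed), 20 each | 200 | 1 − 0.999^200 = 18.1% |

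No rate is given for the other triggers, so they cannot be added.

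**Illustration for efficacy (assumed values).** Suppose one withdrawn patient would have worsened by w SD, and the other nine average no change. The mean over all 10 is −w/10. The mean over the nine is 0. Omission shifts the mean by w/10, which is 0.10 SD for w = 1 and 0.20 SD for w = 2. The standard error of a mean change with 10 patients is 1/√10 = 0.32 SD, so even the larger shift lies below it. Multiplied by the 1.0% chance, the expected shift is about 0.01 × 0.10 = 0.001 SD to 0.01 × 0.20 = 0.002 SD.

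**The case against.** The strongest reply is that the text is silent on follow-up rather than opposed to it. Calling an event grounds for withdrawal is permissive. The Protocol halts data collection expressly only when the participant asks, and it never says that a post-test or adverse-effect visit is cancelled after an investigator-led withdrawal. This stands: a reader might infer that the visits are forbidden or certainly lost, and the Protocol does not say so. But if the rule is discretionary, the investigator decides after seeing the event whether follow-up continues, with nothing written to guide that decision.

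A reader might also infer that the 1-month adverse-effect record would cover only patients free of serious events. That is not supported. Section 13 lists only seizure and new seizure risk factors. Other serious effects discussed in Section 14, such as hearing loss or mania, are not triggers under it, and no 1-month safety summary is planned as such.

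A third tempting reading is that the rule biases efficacy in favour of TMS. The Protocol does not state that withdrawn patients are left out of the analysis, and such handling commonly belongs to the analysis plan. Nor is the direction clear. Section 4 notes that apraxia of speech can result from left hemisphere stroke, so a score after a new stroke may reflect the stroke rather than TMS. With no control group, whether to pool such a score depends on the question being asked.

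Rarity is also a fair point, and it limits the numerical effect. It does not remove the gap, because the rule operates only when such an event has occurred. Nor can an analysis plan recover assessments that were never made.

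**Conclusion.** The point holds as a gap in follow-up. Section 13 ties the listed events to leaving the study, and no section provides for the post-test or the 1-month adverse-effect visit afterwards. The event itself would be seen. Its later course, delayed effects and outcome scores may not be collected.

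The size is modest: 10% of the sample per withdrawn patient, and at most about a 1% chance of any seizure if the quoted risk is per patient. That chance would be higher if the risk is per session, and it is unknown for the other triggers. The effect on the efficacy result is expected to be small. The 0.10 to 0.20 SD shift rests on assumed worsening and on assumed omission from the analysis, so neither its direction nor its presence is established. The case for changing the text rests on safety ascertainment and low cost. When stimulation should stop is a clinical matter and is not judged here.

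**What to change.** In Section 13, leave the listed triggers unchanged, but separate ending TMS from leaving the study. State that patients who meet a trigger stay in follow-up for the already planned post-test and 1-month adverse-effect visit, where they are able, unless they or their proxy decline.

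State also that their adverse effects are reported with all others, and that their outcome scores are reported with the event identified. Leave the handling of those scores in the efficacy summary to the analysis plan. Say when the post-test takes place if the sessions end early.

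The cost is a few sentences in Section 13 and no added visits. The downside is that some patients may decline or be unable to complete testing; recording the reason would keep that visible.

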Based on prior case reports documenting improvement of language function with TMS in PPAOS primary progressive aphasias and post-stroke language disorders, we believe that there is a potential for TMS to improve speech function (as measured by neuropsychological testing and the Apraxia of Speech Rating Scale) in study participants with primary progressive apraxia of speech. This benefit is potentially better than benefits that they could expect to achieve with speech therapy alone (the current standard of care and only other available treatment available outside of a research protocol). However, given that this is a research study, we cannot guarantee any direct benefit.

16) Vulnerable Populations*

Cognitively-impaired adults will be able to participate in this study, provided that the participant has an appropriate proxy who is able to sign a consent form on his or her behalf. We will put in place specific plans to closely monitor these participants (outlined in detail under section 23).

17) Multi-Site Research*

We are not planning to include any additional sites in this study.

18) Community-Based Participatory Research*

We do not have plans for community involvement in the design of this study, at this time.

19) Sharing of Results with Subjects*

We will share the results of the fMRI study, neuropsychological testing, motor cortex excitability findings, and Apraxia of Speech Rating Scale scores with the patients at all follow up visits.

20) Setting

Describe the sites or locations where your research team will conduct the research.

Identification and recruitment of subjects, as well as all follow up visits will take place at the University of Miami Neurology Clinic in the Professional Arts Center building. The address is [name]. TMS will be performed at the Neuromotor Plasticity Laboratory and neuropsychological testing will take place in the neuropsychological testing suite at the same address.

At this time, there are no plans for a community advisory board or research performed at any additional sites.

21) Resources Available

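### Do sections 12 and 19 leave open whether, and when, participants are told their scores, in a way that endangers the 1-month result?

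*Protocol*

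**What the plan says.** Section 12, under its data-monitoring paragraph, begins: "Only authorized personnel will have access to the data collected during the study". It then bars sharing participants' information with other parties unless the IRB approves, and ends: "Research data will not be released to the participants". It makes no exception and does not refer to section 19.

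Section 19 (Sharing of Results with Subjects) says the team will share the fMRI results, "neuropsychological testing, motor cortex excitability findings, and Apraxia of Speech Rating Scale scores with the patients at all follow up visits". It does not refer to section 12.

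Section 8 makes two of these measures the primary outcome: "The primary study endpoint will be improvement on the language performance measured by neuropsychological testing and the Apraxia of Speech Rating Scale".

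On timing, section 7 describes 10 sessions "followed by a second, post-TMS neuropsychological testing session to assess for improvement". It then says: "We will then plan to follow up with patients at 1 month to assess duration of effects of the treatment". A further sentence reads: "The patients will be re-scored using the Apraxia of Speech Rating Scale and will undergo a second neuropsychological testing battery". Section 9 describes the assessment after the sessions in similar terms: "participants will undergo a post-test assessment in which they will be rescored using the Apraxia of Speech Rating scale and reassessed on neuropsychological testing".

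**The concern.** Two things look wrong.

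First, one section forbids releasing research data to participants and another promises them their results. In this study the individual scores are research data, and the Protocol nowhere separates data from results. Taken literally, staff cannot obey both sentences.

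Second, section 19 ties sharing to follow-up visits in the plural, does not list them, and does not say whether feedback comes before or after testing. If a participant learned the post-treatment scores before the 1-month assessment, the knowledge could change effort or expectation at that assessment. The 1-month visit is there to judge how long the effect lasts, and the Protocol describes no control group against which such an influence could be seen. The durability result would then mix persistence of effect with reaction to feedback.

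**Working it through.** The Protocol gives no figure that bears on this point, so the check is a comparison of the text.

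**1. Is the conflict real?** Yes, on the literal wording. Section 12 names participants as not receiving research data. Section 19 lists results that participants will receive. Neither limits the other.

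**2. Can a reader tell which governs?** Ordinarily, yes.
- The section 12 sentence closes a paragraph on who may see the study's data and with whom information may be shared. Its context is custody of records.
- Section 19 deals with nothing except giving results to participants, and it names each type of result. A specific section normally prevails over a general sentence placed elsewhere.

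**3. Does the text put disclosure before the 1-month testing?** It does not show this.
- Section 7 uses follow-up language only for the 1-month visit. The earlier visit is a testing session in section 7 and a post-test assessment in section 9.
- Section 20 places follow-up visits in the neurology clinic and names neuropsychological testing separately, in its own suite. This suggests that a testing session is not itself a follow-up visit. It is not conclusive, because the suite is at the same address and the plural is undefined.
- Scores from the 1-month visit cannot exist until that visit's testing is done. One feedback conversation covering all results therefore falls naturally after the tests.

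**4. What could disclosure change under each reading?**
- *The 1-month visit is the only follow-up and feedback comes after testing:* no outcome remains to be influenced, so the effect is zero.
- *The 1-month visit is the only follow-up and earlier scores are given before testing that day:* effort at that testing could be affected. Size and direction are unknown.
- *The post-test also counts as a follow-up visit:* its scores could be known before the 1-month testing. Size and direction are again unknown, since a good score might encourage and a poor one discourage. Those scores cannot affect the post-test that produced them.

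Under the last two readings, the wording that patients are re-scored suggests that an assessor assigns the Apraxia of Speech Rating Scale. A participant's knowledge would then act mainly through effort. Every participant also knows that he or she is being treated, so expectation already enters all comparisons with baseline.

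**5. What would a rule withholding scores gain and cost?** Under the first reading it changes nothing. Under the second it only reorders one day. Under the third it delays the post-treatment scores by about a month (if the month runs from the post-test), and longer after a second course. Section 7 allows 10 further sessions at a different target for participants without significant benefit. Under the third reading, those participants would have to decide on the offer without the scores they would otherwise have been given.

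**The case for a change.** The strongest case for a change is that both statements are the Protocol's own, so this is not a matter left to a statistical analysis plan, and participants are owed one clear answer. The sentence before the disputed one in section 12 already deals with other parties. The disputed sentence then turns to participants by name, which weakens the view that it concerns only stored records. Section 9 treats the rating-scale and neuropsychological scores as information collected in the study, so they fall within any plain meaning of research data. The plural in sections 19 and 20 also sits awkwardly with a single 1-month visit. A remedy would take one clause, with no extra visits or staff.

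Much of this stands. The wording is untidy, and the order of feedback and testing is not stated. What does not follow is that the results are at risk. An unstated order is not an error: the most natural reading of section 7 puts feedback at the 1-month visit, and no passage puts it earlier. The low cost of a cross-reference does not give it an effect on any estimate. The stricter remedy, withholding outcome scores until the last assessment, goes beyond the conflict. It is a design preference with a cost to participants' informed choice, set against a bias that may be zero and cannot be sized.

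**Conclusion.** The literal conflict between sections 12 and 19 is a clerical slip. It can be tidied by a cross-reference whenever the Protocol is next revised, but it changes no number, analysis or conclusion. The timing point is a gap that staff can fill sensibly by testing first and giving feedback afterwards. Followed that way, at the 1-month visit, the study's results are no less sound. The effect on the durability result is then zero; under the other readings it cannot be determined from the document. Withholding scores until the last assessment is a debatable trade-off, not a correction.

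This rests on two readings that the text supports but does not state outright: that section 19 governs what participants are told, and that the 1-month visit is the follow-up visit meant there. It also takes the re-scoring sentence in section 7 to refer to the 1-month visit. That is the natural reading from its position, although the sentence carries no time of its own.
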